11.2.4.9. EQ-5D (Quality of Life)

The 24 months follow up assessment of the EQ-5D will be analyzed as follows.

The EQ-5D consists of 5 items with 3 possible answers each and an EQ visual analogue scale. For each item (Mobility, Looking after myself, Doing usual activities, Having pain or discomfort, Feeling worried, sad or unhappy) the count and percentages of each possible answer will be presented per age group (the analysis will be done per age at randomization) and per treatment group. The difference between treatment groups will be tested using a chi square test (or Fishers' exact test in case of small expected cell counts).

The values of the EQ visual analogue scale (EQ VAS) will be presented by treatment group using descriptive statistics. The mean EQ VAS values between treatment groups will be compared by a one-way analysis of variance.

Additionally, the single summary index will be analyzed analogously as the EQ VAS.

The linear regression model with the single summary index as target variable will be applied for testing the statistical significance of the difference in scores between NexoBrid and SoC treatments at 24 months. Adjustment will be made for any imbalance between the groups in treatment center and overall treated %TBSA.

11.2.5. Exploratory Analyses

11.2.5.1. POSAS

The POSAS will be evaluated on a subject level. The POSAS for target wounds will be calculated as outlined in Section 10.3.5.7 and will be presented by treatment group using descriptive statistics. The mean POSAS values between treatment groups will be compared by a one-way analysis of variance.

The analysis will be repeated for the patient scale and for the observer scale separately.

The analyses will be conducted for the POSAS assessments (both on-site and remotely collected) of 18 and 24 months.

In addition, the analysis will be repeated excluding subjects with remotely collected data.

11.2.5.2. MVSS (target wounds)

The MVSS for target wounds (analyzed on a subject level) at 18 months (both on-site and remotely collected) will be calculated as outlined in Section 10.3.4.2 and will be presented by

treatment group using descriptive statistic. The mean MVSS values between treatment groups will be compared by a one-way analysis of variance.

In addition, the analysis will be repeated excluding subjects with remotely collected data.

11.2.6. Pharmacokinetic Variables

Not applicable. All pharmacokinetic data was already analyzed in the first stage analysis (see Section 11.1.7).

11.2.7. Multicenter Data

See Section 11.1.8.

11.2.8. Handling of Multiple Comparisons

Not applicable. All testing done during this second stage analysis is exploratory in nature. So no adjustment for multiplicity is needed.

11.2.9. Interim Analysis

No interim analyses will be performed.

11.2.10. Stratification

See Section 11.1.11.

13.1. Randomization Algorithm

Treatment allocation is performed using the method of minimization with stratification by the factors A, B, C and D described in Section 11.1.11 above: age group (A), overall %TBSA of all TW wounds (B), overall % of FT area (C) and clinical center (D).

At any point in the trial a new patient is to be entered into the trial, the four above described factors have to be collected for that particular patient. The value for each factor of this patient is denoted by Ai, Bi, Ci and Di, respectively, where i is corresponding to the value of each factor, which is i = 1, 2, 3, 4 for factor A, i = 1, 2 for factors B and C and i = 1,..., m for factor D, with m being the number of participating clinical centers.

For example: a patient, of 25 months of age with overall total area of burns of 4% - 9% and a proportion of the FT area of ≥20% is to be recruited in the 5th clinical center. This would lead to (A2, B1, C2, D5).

The different treatment groups are denoted by j where j=1 corresponds to the NexoBrid group, j=2 to the SoC group. The numbers of patients in each stratum A, B, C, D receiving the j-th treatment and having the i-th factor are denoted by Aij, Bij, Cij and Dij.

When a new patient is to be allocated a treatment, a score for each treatment group j is determined based on the patient's specific factors and on the number of patients already allocated to the treatments. This score is denoted by Nj and is calculated by the sum of Aij, Bij, Cij and Dij. In our example the new patient has the factors A2, B1, C2, D5, hence the numbers of patients for each of these factors in treatment group j=1 which is the NexoBrid treatment are A21, B11, C21, and D51 respectively and the score N1 can be calculated as N1 = A21 + B11 + C21+D51. The score for the SoC treatment N2 can be calculated similarly: N2 = A22 + B12 +C22+D52. To determine which treatment has to be allocated to the next patient, these two scores are compared.

The trial started with the following method of treatment allocation. Since a 1:1 randomization is used in this trial, the patient is allocated to the treatment group with the smallest value among these two score values (strict minimization). Thus, the allocation decision is based on min (N1,

N2). If N1 equals N2, then simple randomization between the treatments is used with probabilities p1=p2=0.5 for each treatment.

On 19th May 2017 it was decided to modify the method of treatment allocation in the following manner. The strict minimization method (described above) assigned the treatment to a patient so as to reduce the imbalance between the treatment groups at any stage. Only if allocating to either treatment yielded the same level of imbalance would the treatment be assigned at random (with a probability of 0.5). A modification is that the algorithm would henceforth assign with probability 0.9 the treatment that reduces the imbalance and with probability 0.1 the treatment that increases the imbalance (minimization with a random element). As before, if both treatment allocations lead to the same imbalance, randomization with probability 0.5 will be used. Thus, using the same notation as above, if N1 < N2 then treatment 1 is allocated with probability 0.9 and treatment 2 with probability 0.1. If N1 = N2, then treatment 1 is allocated with probability 0.5 and treatment 2 with probability 0.5.

13.2. Potentially Clinically Significant Thresholds

13.2.1. Vital Signs

The burn injury and any treatments administered before study treatment may affect body systems and their regulatory functions, including heart rate, blood pressure, fluid balance, and temperature. Therefore, measurements of vital signs might be abnormal prior to study treatment administration. In addition, only a few hours elapse between baseline and the following time point when vital signs are measured.

In order to capture significant changes in vital signs that might be related to treatment, potentially clinically significant (PCS) thresholds for vital signs were defined using both the numerical value of the parameter and a clinically significant change from baseline.

Vital Sign	Criterion	Explanation			
(unit)	value				
Systolic	Low PCS: <	Low PCS is based on PALS Guidelines depending upon age:			
Blood Pressure	age defined threshold	Term neonates (0 to 28 days): The systolic BP is < 60 mmHg			
(mmHg)	and	Infants (1 to 12 months): Systolic BP is < 70 mmHg			
	decrease	Children 1 to 10 years (5th BP percentile): Systolic BP is < 70			
	>10%	mmHg + (age in years x 2)			
		Children > 10 years: Systolic BP is < 90 mmHg			
	High PCS:≥	High PCS is based on the normal blood pressure levels for			
	20% above	boys and girls by age and height percentile. The 95 th percentile			
	the 95 th	is taken for the 50 th height percentile [23].			
	percentile	95 th percentile SBP for Girls (mmHg):			
	for age/gender	1y-103			
	and	2y-106			
	increase	3y-108			
	>10%	4y-109			
		5y-110			
		6y-111			
		7y-112			
		8y-113			
		9y-114			
		10y-116			
		11y-118			
		12y-122			
		13y-124			

14y-125
15y-126
16y-127
17y-127
95 th percentile SBP for Boys (mmHg):
1y-103
2y-106
3y-107
4y-108
5y-109
6y-111
7y-112
8y-114
9y-115
10y-116
11y-118
12y-121
13y-125
14y-130
15y-132
16y-134
17y-135
The increase from baseline for High PCS is used to capture
significant changes, since elevated blood pressure might be

		present prior to study treatment due to effects of the burn injury		
		and any pre-study treatments.		
Respiratory	Low PCS:	Low Respiratory Rate PCS is based on PALS Guidelines		
Rate	<age< td="">depending upon age:	</age<>	depending upon age:		
(breaths/mi	defined			
n)	threshold	Infant, 30		
	and	Toddler, 24		
	decrease	Preschooler, 22		
	>10%	School-aged, 18		
		Adolescent, 12		
		Respiration can be compromised following burn injury [24].		
	High PCS:	High Respiratory Rate PCS is based on PALS Guidelines		
	> age	depending upon age:		
	defined	Infant, 60		
	threshold and	Toddler, 40		
	increase	Preschooler, 34		
	>10%	School-aged, 30		
		Adolescent, 16		
Temperatur	Low PCS:	Temperature <36°C was used in the NexoBrid protocols (eg,		
e (°C)	<36 and	CIDS) to define hypothermia.		
	decrease	A temperature of 35°C is commonly used in the definition of		
	>0.5	hypothermia [25], which is lower than the PCS threshold and		
		therefore encompassed by it.		
		Temperature <36°C was found to be useful as a predictor for sepsis [26]		
 	l .			

	High PCS: >39 and increase >0.5					
Heart rate (beats/min)	Low PCS: < lower threshold for age while awake and decrease >10%	Normal Pulse Rate according to PALS will be defined depending upon age, while awake: Newborns up to 3 months old, 85–205 Age 3 months to 2 years old, 100–190 Ages 2 to 10, 60–140 Children aged 10 years and above, 60–100				
	High PCS: > upper threshold for age while awake and increase >10%	Normal Pulse Rate according to PALS will be defined depending upon age, while awake: Newborns up to 3 months old, 85–205 Age 3 months to 2 years old, 100–190 Ages 2 to 10, 60–140 Children aged 10 years and above, 60–100				

13.2.2. Laboratory Parameters

Burn injury affects almost all body systems. Therefore, a wide range of laboratory parameters may be affected, which may be abnormal prior to study treatment. In addition, only a few hours elapse between baseline and the following time point when laboratory parameters are measured.

For these reasons, in order to capture significant changes in laboratory parameters that might be related to treatment, PCS thresholds for laboratory parameters were defined using both the numerical value of the parameter and a clinically significant change from baseline.

Many of the PCS definitions for laboratory values below are based on Grade 2 definitions from the CTCAE version 5.0 [28]. As in the CTCAE, multiplication of the baseline value is used to define high PCS for several parameters in order to capture significant changes from baseline, as the lab result may be abnormal at baseline.

Test (unit)	Criterion	Explanation		
	value			
Serum Chemist	ry			
Creatinine (umol/L)	>1.5x ULN if Baseline ≤ ULN or >1.5x Baseline	Acute kidney injury is a common complication in burn patients. Early kidney damage in the burn patient might be due to hypovolemia, inflammatory processes, tissue destruction and release of denaturated proteins, iatrogenic causes (eg, nephrotoxic agents), and/or cardiac dysfunction. The High PCS definition is based on the definition of Stage 1 acute kidney injury and on the lower limit of the CTCAE Grade		
	Baseline > ULN.	2 definition [28]. The approach of using multiplication of baseline value when baseline is already elevated is used in the CTCAE Grade 2 definition and in the RIFLE risk definition in the Acute Dialysis Quality Initiative (ADQI) criteria for the definition and classification of AKI [29].		
Glucose (mmol/L)	<3.00 mmol/L High PCS: >11.10 mmol/ L and increase	Low PCS is based on the upper limit of CTCAE definition of Grade 2 hypoglycemia [28] [30] Hyperglycemia is common in burn patients [31]. High glucose values >200 mg/dL (>11.10 mmol/L) are related to higher rates of infection and mortality among burn and trauma patients [32] [33]. In addition, glucose >200 mg/dL is one of		

		the triggers for the definition of sepsis according to the American Burn Association [27]
Total Bilirubin (umol/L)	High PCS: >1.5x ULN if Baseline ≤ ULN or >1.5x Baseline value if Baseline > ULN	Based on the lower limit of the CTCAE Grade 2 definition [28].
Alkaline Phosphatase (U/L)	>2.5x Age/ Gender ULN if Baseline ≤ ULN or >2.5x Baseline	Based on the lower limit of the CTCAE Grade 2 definition [28], and age normal range U/L of study laboratory: 7-365 days: 50-270 1-2y: 50-270 3-12y: 60-415 13-15y male: 60-500, 13-15y female: 60-350 16-19y male: 30-225, 16-19y female: 30-165
SGPT (ALT) (U/L)	High PCS: >3x ULN if Baseline ≤ ULN or >3.0x Baseline value if	Based on the lower limit of the CTCAE Grade 2 definition [28]. Alanine aminotransferase (ALT) levels can increase immediately after burn injuries [34] and therefore might be increased already at baseline.

	Baseline	
	> ULN	
SGOT (AST) U/L	>3x ULN if	Based on the lower limit of the CTCAE Grade 2 definition. Aspartate aminotransferase (AST) levels can increase immediately after burn injuries [34] and therefore might be increased already at baseline.
Albumin (g/L)	≤25 g/L and Decrease	Hypoalbuminemia is common in burn patients. Hypoalbuminemia might occur in burn patients due to protein loss, an inflammatory process that affects plasma protein synthesis in the liver, and/or higher vascular permeability in burn wounds that causes exudation with protein loss. The CTCAE definition of Grade 2 hypoalbuminemia is albumin levels between 2 to 3 g/dL (20-30 g/L) [28].
		Since the lower limit of normal laboratory ranges of the study is around 3g/dL (7days-2y: 3-5g/dL, 3-199y: 3.2-5g/dL), PCS value lower than normal was taken. In the literature, morbidity corresponds to albumin <20 to 25
		g/L [35] [36]. Oncotic activity remains physiologically adequate at albumin ≥2 g/dL. An albumin level ≤20 g/L is commonly agreed by practitioners to trigger administration of intravenous albumin [37].

Calcium (Ca ⁺⁺),	Low PCS:	Please refer to corrected calcium below
	<2 mmol/L and	
(mmol/L)	decrease	
	≥10%	
	=1070	
	High PCS:	Please refer to corrected calcium below
	>2.9 mmol/L	
	and increase	
	≥10%	
Corrected	Low PCS:	Low calcium levels are seen in burn patients and might be due
Calcium (Ca ⁺⁺),		to extracellular-intracellular shifts, calcium accumulation in
(mmol/L)		erythrocytes, increased urinary excretion, and/or calcium loss
(in tissue exudates.
	_10,0	
		Calcium levels are related to albumin levels, which are
		frequently decreased in burn patients.
		Low PCS is based on the upper limit of CTCAE definition of
		Grade 3 hypocalcemia [28].
	High DCC:	Llimb DCC is based on the lawer limit of CTCAE definition of
		High PCS is based on the lower limit of CTCAE definition of
		Grade 2 hypercalcemia [28].
	and increase	
	≥10%	
Sodium (Na ⁺)	Low PCS:	Low PCS is based on the upper limit of CTCAE definition of
(mmol/L)	≤129 and	Grade 2 hyponatremia [28].
	decrease >4	
	High PCS:	High PCS is based on the lower limit CTCAE definition of
		Grade 2 hypernatremia [28].
	increase ≥5	
		Studies have shown increased morbidity and mortality for
		patients with hypernatremia defined as >150 meq/L (mmol/L)
		[38].
		 

Potassium (K ⁺)	Low PCS: <3	Low PCS is based on the upper limit of CTCAE definition of			
(mmol/L)	and decrease	Grade 3 hypokalemia [28].			
	≥10%	Since the normal laboratory ranges of the study are between			
		3.5-5.5mmol/L (0-2y 3.8-5.5mmol/L, 3-12y 3.5-5.5mmol/L, 13-			
		199y 3.5-5.3mmol/L), PCS value lower than normal			
		corresponding to Grade 3 was taken.			
	High DCC	Limb DCC is based on the lower limit of CTCAE definition of			
		High PCS is based on the lower limit of CTCAE definition of			
		Grade 3 hyperkalemia [28].			
	increase ≥10%	Since the normal laboratory ranges of the study are between			
		3.5-5.5mmol/L (0-2y 3.8-5.5mmol/L, 3-12y 3.5-5.5mmol/L, 13-			
		199y 3.5-5.3mmol/L), PCS value higher than normal			
		corresponding to Grade 3 was taken.			
Hematology					
	D00	h - 500			
Hemoglobin		Low PCS was set to be in line with the limit at which blood			
(g/L)		transfusion is recommended [39]. According to current clinical			
		recommendations for burn patients, blood transfusion is			
	≥10%	administered when hemoglobin is below 7.0 to 8.0 g/dl (70-80			
		g/L) [40].			
		For most patients, restrictive RBC transfusion strategy (ie,			
		Hgb of 7 g/dL (70g/L) as the transfusion threshold) rather than			
		more liberal transfusion strategies is recommended. Slightly			
		higher limit was taken as PCS since higher Hgb levels may be			
		appropriate in certain conditions [41]			
Platelets		Low PCS is based on the upper limit of CTCAE Grade 2			
(10 ⁹ /L)	<75 and	definition [28].			
	decrease				
	≥10%				

		
	High PCS:	Platelet levels greater than the upper limit of normal but below
	>600 and	700 are regarded as mild thrombocytosis and do not require
	increase >10%	treatment. Platelet levels >700 are defined as moderate
		thrombocytosis [42]
		Increased platelet turnover might be seen in burn patients due
		to a fall in platelet count followed by an increase in platelet
		production and a rebound thrombocytosis [43]
Total	Low PCS: <	The Low PCS is based on the normal limits of total leukocytes
Leukocyte	=20% age	depending upon age;
(10 ⁹ /L)		60-179days: 5-18
	threshold	180days-1y: 5-17,
		2-5y: 5-16,
		6-11y: 4.5-13.5,
		12-17y: 4.5-13
	High PCS: ≥	The high PCS is based on the normal limits of total leukocytes
	20% age	depending upon age;
	related threshold	60-179days: 5-18
	unesnoid	180days-1y: 5-17,
		2-5y: 5-16,
		6-11y: 4.5-13.5,
		12-17y: 4.5-13
Neutrophil	Low PCS: <1.5	Low PCS is based on the common definition of neutropenia
(10 ⁹ /L)		and the upper limit of CTCAE Grade 2 definition [28].
	High PCS:	Neutrophil count might increase following burn trauma,
	≥20% upper	surgical procedures, or stress [44]
	limit of normal	
	White Cell	

		 
	Count upon	Normal White Cell Count upon age group:
	age group and	90-179days: 1-8.5
	increase ≥	
	10% from	180-364days: 1.5-8.5
	baseline	1-199y: 1.8-8
Coagulation		
International	High PCS >1.5	A common normal range of INR was set to be up to 1.2, since
Normalized	if Baseline is	normal ranges for local labs were not available for all sites.
Ratio (INR)	≤1.2	The PCS is based on the lower limit of the CTCAE Grade 2
ratio	>1.5x Baseline	
		deminion [20].
	if Baseline is	
	>1.2	
Activated	>1.5x ULN if	Derived from the lower limit of CTCAE Grade 2 definition [28].
Partial	Baseline	This limit was used in the DETECT protocol to define a
Thromboplastin	< ULN	significant increase [45]
Time (PTT)	>1.5 x	
(sec)		
(550)	Baseline if	
	Baseline	
	> ULN	

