For each patient a binary (yes/no) variable will be computed indicating whether this patient had a hospital readmission or not. Additionally, for each hospital readmission, a binary (yes/no) variable will be collected indicating whether this readmission was planned or not. A readmission will be considered as being planned when the reason for readmission was indicated as "planned wound management" or "scar modulation" in the eCRF. Readmissions for which the reason was given as "AE" in the eCRF are considered as being unplanned. Hospital readmission for which the reason is given as "other" will be reviewed by the sponsor in order to decide whether they are to be classified as planned or unplanned.

Furthermore, a variable giving the number of planned hospital readmissions and a variable giving the number of unplanned readmissions will be computed for each patient.

Relative and absolute frequencies of hospital readmission (overall, planned, and unplanned) will be calculated per treatment arm.

For subjects who discontinued study participation during the efficacy assessment period, it is not known whether a(nother) readmission occurred and relevant data are missing.

Consequently, the variable is set to missing for all those subjects except for "Lost-to-follow-ups" who completed the eschar removal treatment. The exception is done under the assumption that subjects who are lost to follow up would have come back for readmission if this had been necessary (Without this exception a lot of information would have been lost in MW2010 since the percentage of subjects with re-admission is higher for "Lost-to-follow-ups" then for the rest of the population).

Change in PTT/INR

Change in PTT/INR will be computed as PTT/INR on $4h \pm 15$ min post first application (NexoBrid arm) respectively to 4h post first SoC treatment (SoC arm) minus PTT/INR pre the respective procedure for each patient.

For the classification of normal and abnormal PTT/INR values (low or high), the reference limits of the local labs will be used. If INR reference ranges will not be available for specific sites, common normal range of 0.8-1.2 will be used for these sites [19].

In addition, for each subject, for each parameter (INR/PTT) a variable will be computed, indicating whether the 4 hour post first treatment measurement was post treatment potentially clinically significant high (pCS high) or post treatment potentially clinically significant low (pCS low).

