11.1.5.14. Change in PTT/INR

Change in INR/PTT will be evaluated at 4h post first treatment. For the classification of normal and abnormal INR/PTT values, the reference limits of the local labs will be used (see also Section 10.3.4.4).

The following tables will be produced for INR and PTT:

- Shift tables indicating shifts from baseline (low/normal/high) to post first treatment (low/normal/high) as well as a listing of subjects experiencing shifts from low/normal to high
- Shift tables indicating shifts from baseline to post first treatment potentially clinically significant result as well as a listing of subjects experiencing such shifts. For the definition of pCS high and pCS low, see Section 13.2.2.

Only subjects with non-missing pre and post values will be considered for the analysis.

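### The INR high-PCS rule steps from above 1.5 to above 1.8 once baseline passes 1.2, so some children with a higher INR and a larger rise go unflagged while others with less are flagged

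*SAP*

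**What the plan says.** The introduction to SAP 13.2.2 states that "PCS thresholds for laboratory parameters were defined using both the numerical value of the parameter and a clinically significant change from baseline". It adds that "multiplication of the baseline value is used to define high PCS for several parameters in order to capture significant changes from baseline", because a result may already be abnormal before treatment.

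The INR row has two branches. With baseline at or below 1.2, high PCS is a value above 1.5. With baseline above 1.2, it is ">1.5x Baseline". The explanation column says: "A common normal range of INR was set to be up to 1.2, since" local ranges were missing at some sites. It bases the rule on a cited toxicity grading.

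The PTT, creatinine, bilirubin, alkaline phosphatase and ALT rows are built differently. They use a multiple of the upper limit of normal (ULN) when baseline is within range, and the same multiple of baseline when it is above.

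For the ordinary low/normal/high classes, SAP 10.3.4.4 uses each local laboratory's limits. Only where a site has none does it fall back: "common normal range of 0.8-1.2 will be used for these sites".

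SAP 11.1.5.14 says how the results are shown. "Change in INR/PTT will be evaluated at 4h post first treatment", with two outputs:
- a low/normal/high shift table, "as well as a listing of subjects experiencing shifts from low/normal to high";
- a second table, which cross-classifies the baseline class against the PCS flag and has its own listing of the children concerned.

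SAP 11.1.12 repeats these analyses in each age subgroup.

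**The concern.** A flag that combines a value with a change should not rank a smaller rise to a lower value above a larger rise to a higher one. Here it can, because the lower branch is an absolute 1.5 and the upper branch begins at 1.5 times 1.2.

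The other planned INR outputs recover such a child only in part. If the child is already high at baseline by the limits that apply at the site, the low/normal/high table shows an undifferentiated high-to-high count, and the accompanying listing leaves the child out. SAP 10.3.4.4 defines the change in INR, but 11.1.5.14 specifies no summary of it. INR is a local laboratory test (SAP 7.2.3.5), so the central-laboratory tables in 11.1.5.5 do not cover it. What remains is the general case-wise listing mentioned in SAP 11.

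At stake is how fully the PCS table and listing show INR rises in children who start above 1.2, overall and by age group.

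**Working it through.** **Inputs.** The two branches and the cut point of 1.2 come from SAP 13.2.2. The rule carries no sample size, test or power, so there is no planned figure to reproduce.

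**Rule.** With baseline b, the post-treatment value must exceed T(b), where T(b) = 1.5 if b ≤ 1.2, and T(b) = 1.5 × b if b > 1.2.

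| Baseline b | T(b) | Rise needed, T(b) − b | Rise as % of b |
|---|---|---|---|
| 1.00 | 1.50 | 0.50 | 50% |
| 1.10 | 1.50 | 0.40 | 36% |
| 1.20 | 1.50 | 0.30 | 25% |
| 1.21 | 1.815 | 0.605 | 50% |
| 1.30 | 1.95 | 0.65 | 50% |
| 1.40 | 2.10 | 0.70 | 50% |

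Between 1.20 and 1.21 the threshold rises by 1.815 − 1.50 = 0.315, and the required percentage rise doubles.

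**Comparison with the ULN form.** The PTT-type rule is 1.5 × ULN, then 1.5 × baseline. With ULN = 1.2 it gives 1.5 × 1.2 = 1.80 at baseline 1.20 and 1.815 at 1.21. The difference is 0.015, so there is no step.

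**Pairs.**

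| Baseline → post | Rise | T(b) | Flagged? |
|---|---|---|---|
| 1.20 → 1.51 | 0.31 (26%) | 1.50 | yes |
| 1.21 → 1.80 | 0.59 (49%) | 1.815 | no |
| 1.30 → 1.90 | 0.60 (46%) | 1.95 | no |
| 1.40 → 2.05 | 0.65 (46%) | 2.10 | no |
| 1.30 → 1.96 | 0.66 (51%) | 1.95 | yes |
| 1.40 → 2.20 | 0.80 (57%) | 2.10 | yes |

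The second to fourth rows exceed the first in final value, absolute rise and relative rise, yet only the first is flagged. The last two rows show where the gap ends. For b > 1.2 the unflagged band is 1.5 < post ≤ 1.5 × b, with width 1.5 × (b − 1): 0.45 at b = 1.30 and 0.60 at b = 1.40.

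**Can the number affected be estimated?** The documents give no INR data. An illustrative simulation assumed 145 children, mean baseline 1.05 to 1.25 (SD 0.12) and mean log ratio of post to baseline 0.05. The share of simulated trials in which the highest post-treatment INR was unflagged was 80–99% when the SD of the log ratio was 0.1, 11–14% at 0.2, and under 0.3% at 0.3. That count does not require the highest value to exceed 1.5. The answer is set by the assumptions.

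**The case against.** The strongest defence is that SAP 13.2.2 gives a reason for baseline multiples: when a child starts abnormal, a proportional rise is the sensible signal. That stands as a reason for the upper branch. It does not explain why the lower branch is an absolute 1.5 rather than 1.5 times the assumed limit of 1.2. The step may come from the cited toxicity grading, which cannot be checked from these documents. Even so, the inversion would remain in this trial's output.

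Second, the safety outcome named in the protocol synopsis and SAP 7.2.3.6 is change in INR/PTT and incidence of change to above the ULN. The incidence part comes from the low/normal/high table, which does not use the PCS cut. This is correct and limits the point to a further descriptive display.

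Third, whether the child in the 1.30 → 1.90 example is high at baseline depends on the site. If the local upper limit is 1.3 or above, the child is normal at baseline, and the low/normal-to-high listing picks the child up provided 1.90 exceeds that limit. This stands. The loss from that listing applies only to children classed as high by the limits in force. It also shows a mismatch: local limits govern the classes where they exist, while the PCS cut is 1.2 at every site.

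A reader might infer that the rule generally misses the children with the highest INR. The documents do not support that, because above baseline 1.2 every value beyond 1.5 times baseline is flagged. Nor do they support a claim that NexoBrid's coagulation effect will be under-counted by any stated proportion, since no INR distribution is given.

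**Conclusion.** The INR rule is discontinuous at baseline 1.2, and this follows exactly from the SAP's own text. The threshold moves from 1.50 to above 1.80, and children with baseline above 1.2 whose INR ends above 1.5 but not above 1.5 times baseline are unflagged, while some children with lower values and smaller rises are flagged. The ULN-based rows named above have no such step. The PTT row leaves baseline equal to ULN unassigned, and the AST row is incomplete in the available text, so it is not relied on.

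The same rule applies to both arms, and no hypothesis test uses it. The primary and secondary results are untouched. The consequence is an inconsistent PCS table and listing for INR, of unknown size, which is cheap to correct.

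**What to change.** 1. In SAP 13.2.2, reconcile the two INR branches so that the flag does not step at 1.2, or state why the step is intended. More than one form would remove it: the ULN form used for PTT would give fewer flags, and a single cut with a required change would give more. The documents do not select one.
2. In either case, tabulate the two criteria already in the SAP (post above 1.5, and post above 1.5 times baseline) as separate rows for all children whatever their baseline, by arm and baseline category.
3. In SAP 11.1.5.14, extend the listing to children already high at baseline whose INR rises further.

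This needs no new data. It costs one extra row and more listed cases in both arms. The split by baseline category is needed to read the rows. The first includes a child who starts above 1.5 and does not change (1.60 → 1.60). The second includes a child with a low baseline who ends below 1.5 (0.80 → 1.30, against 1.5 × 0.80 = 1.20).
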